5.3 Eltrombopag

Subjects will initiate eltrombopag at a starting daily dose as detailed in Table 3, according to age and ethnicity. Subjects between 12 and 17 years of age will receive the adult dose of 150 mg. Those between 6 and 11 will start at 75 mg, and children between 2 and 5 years of age will be started at 2.5 mg/kg (Table 3). To adjust for the higher expected exposure in children of East Asian and South East Asian ancestry, the starting dose for East Asian and South East Asian subjects between 12 and 17 years of age will be 75 mg once daily. For East Asian and South East Asian subjects between 6 and 11 years of age, the starting dose will be 37.5 mg once daily, and for children between 2 and 5, the starting dose will be 1.25 mg/kg (Table 3). Eltrombopag will be administered orally as tablets or an oral suspension from sachet of eltrombopag powder. Each 25 mg Pfos sachet contains eltrombopag olamine equivalent to 25 mg of eltrombopag free acid. If a child's dose is based on body weight and needs a dose of 28 mg, then dose only single sachet that provides 25 mg dose. However, if the child needs a dose of 29 mg or greater, then the suggestion is to start using the second sachet. This is mainly suggested to prevent the wastage of medicine by opening a second sachet to meet the additional 1-3 mg dose. Dosing 25 mg where a patient needs 28 mg should not have a significant impact on PD response. If an adult receives the oral suspension administration of eltrombopag, the required number of sachets will be used to administer the below adult doses.

Table 3. Dosing according to age and ethnicity

Age groups	Daily dose
Non-Asian	
12-85	150 mg
6-11	75 mg

Age groups	Daily dose
2-5	2.5 mg/kg
East Asian, South East Asian	
12-85	75 mg
6-11	37.5 mg
2-5	1.25 mg/kg

Eltrombopag may be taken on an empty stomach (1 hour before or 2 hours after a meal) or with food containing little (<50 mg) or preferably no calcium or dairy products. Allow at least a 4-hour interval between eltrombopag and other medications or products containing polyvalent cations (e.g. calcium, magnesium, aluminum, zinc, selenium or iron) such as antacids, dairy products, and mineral supplements to avoid significant (70-75%) reduction in eltrombopag absorption due to chelation.

Dose delay or dosing interruptions:

Cohort 1:

Eltrombopag dose may be interrupted when clinically indicated at the discretion of the investigator. Interruptions will be recorded in the medical record.

Cohort 2, 3, Extension Cohort and Exploratory Laboratory Cohort:

The first dose of eltrombopag may be delayed if it is clinically indicated or other unforeseen events affect the start of eltrombopag (for example weather related) at the discretion of the investigator.

Eltrombopag dose may be interrupted when clinically indicated at the discretion of the investigator (for example if the patient is in the intensive care unit and unable to take PO medications). For subjects on cohort 2, if eltrombopag dosing is delayed or interrupted for more than 1 week (7 days) and the interruption is not the result of a severe adverse event related to eltrombopag, then the subject will receive additional eltrombopag in order to receive a total of 10 weeks as originally planned for cohort 2.

Medication dosing errors, dose delays or dosing interruptions:

Interruptions such as delays in request for medication refills or medication errors by subjects will be recorded in the medical record.

5.4 Dose Adjustments of Eltrombopag

The daily dose of eltrombopag will be decreased according to the following rules:

Platelet Count	Dose Adjustment or Response
>200,000/ μ L (untransfused) at any time on study	Decrease dosage by 25mg every 2 weeks to lowest dosage that maintains platelet count \geq 50,000/ μ L. In children under 12, the dose will be decreased by 12.5 mg.
>400,000/ μ L (untransfused) at any time on study	Discontinue eltrombopag for one week, if platelets fall to <200,000/ μ L; restart at dosage decreased by 25 mg/day (or 12.5 mg in children under 12).

5.5 Dose Delays, Modifications or Discontinuation of Eltrombopag for Non-Hematologic Side Effects

5.5.1 Infection: Subjects who experience an infection requiring intravenous antibiotics will not have eltrombopag discontinued. If the subject experiences infection severe enough to require vasopressors or intubation, the drug will be withheld until the subject is stable.

5.5.2 Liver function abnormalities:

Cohorts 1 and 2:

In the event of an increase in the ALT level to > 6 times the ULN, subjects will return to clinic or have blood tests drawn by their home physician every 3-4 days. If the ALT remains > 6 times the ULN on a second blood test, eltrombopag will be discontinued until ALT is < 5 times the ULN. Eltrombopag will be restarted at a dose level 25 mg/day lower than the prior dose. If liver test abnormalities return to an ALT of > 6 times ULN on this reduced dose, the eltrombopag dose will be reduced by 25 mg/day until there is reduction of ULN to < 5 ULN.

Cohort 3 Extension Cohort and Exploratory Laboratory Cohort:

Transient hepatotoxicity is an expected and common side effect of h-ATG that occurs during the first 14 days following the start of h-ATG administration. In the event of an increase in the ALT level to > 6 times the ULN during Days 1 – Days 14, eltrombopag will be held until ALT is < 5 times the ULN and then resumed at the same dose. If the ALT rises to > 6 times ULN after resuming eltrombopag (and is not attributable to other inciting factors such as serum sickness, sepsis, or azole antifungal agents) then the ALT will be monitored at least every 3-4 days. If the ALT remains > 6 times the ULN on repeat blood tests, eltrombopag will be stopped until the ALT is < 5 times the ULN. Then eltrombopag will be restarted at a dose level that is 25 mg/day lower than the prior dose. If liver test abnormalities return to an ALT of > 6 times ULN on this reduced dose, the eltrombopag dose will be reduced by 25 mg/day until there is reduction of ULN to < 5 ULN.

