2.9.4 Justification for adding Laboratory Exploratory Cohort

We currently have accrued 178/182 patients to our protocol, 12-H-0150. Among these patients, 86 compose an extension cohort; the primary aim of extension of the study was to obtain more precise data regarding important secondary endpoints and to collect more pharmacokinetic samples.

We now propose an extension to add 25 subjects to perform novel laboratory experiments using *fresh* bone marrow samples obtained at the time of diagnosis and prior to institution of definitive therapy. **These experiments will not be feasible in our upcoming treatment naïve SAA protocol because we plan to initiate treatment remotely, and thus will not be collecting baseline marrow/blood samples for research.**

T cell mediated immune destruction of hematopoietic stem and progenitor cells (HSPCs) is the pathophysiology of SAA, but precise mechanisms have not been characterized, nor have biomarkers been identified. We intend to elucidate the pathophysiology of SAA using advanced single-cell methodologies (scRNA-seq), a technique that allows high resolution whole transcriptome profiling of the individual cells, and time of flight cytometry (CyTOF), a novel deep-phenotyping technique using multiparameter mass cytometry. scRNA-seq will be used to study the transcriptome of HSPCs and enriched T cells, and T cell clonality in patients with newly diagnosed severe aplastic anemia (SAA). CyTOF will enable high resolution characterization of HSPCs, immune cells especially regulatory T cell subsets, and other marrow populations simultaneously based on a range of cell surface and intracellular markers, to explore the relationship of bone marrow microenvironment and hematopoiesis in patients with SAA. If a biomarker or genetic signature is identified from these experiments, further experiments could be performed on larger cohort of frozen samples using simpler methods, such as standard flow cytometry or multiplex polymerase chain reaction (PCR).

Our aims are to:

- (1) Identify characteristic cell population in treatment naïve SAA, provide a comprehensive view of active marrow process in SAA patients at both cellular and molecular levels
- (2) Infer potential autoantigens from the expanded clonal T cells, perform integrated analysis of receptors and ligands of T cells and HSPCs

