5.9 Permitted Supportive Care

- Transfusion support (blood and platelets) as clinically indicated.
- Hematopoietic growth factors (e.g., G-CSF, GM-CSF, or erythropoietin) if deemed necessary by the investigator or treating physician. Romiplostim (N-Plate) or IL-11 (Neumega) should not be administered.
- Estrogens or combination OCP's as indicated for uterine bleeding

5.10 Concurrent Medications:

Cyclosporine/magnesium: Subjects will be on chronic CsA therapy targeting a stable drug level as long

as eltrombopag is administered 4 hours after oral magnesium given to counteract magnesium-wasting on CsA. Magnesium supplementation will not be given concurrently with eltrombopag as it may interfere with eltrombopag's absorption. The drug-drug interaction potential between eltrombopag and CsA is unknown. Both CsA and eltrombopag are inhibitors of OATP and BCRP drug transporters, and eltrombopag is a substrate of BCRP in vitro. It is not known if the combination will result in any PK changes to either drug. Subjects will be monitored for signs of CsA toxicity during the study, and therapeutic drug monitoring can be instituted as required. In the event of liver function abnormalities as a consequence of a drug-drug interaction between eltrombopag and CsA, eltrombopag will be dose-reduced according to Section 5.5.2.

Rosuvastatin: In vitro studies demonstrated that eltrombopag is not a substrate for the organic anion transporter polypeptide, OATP1B1, but is an inhibitor of this transporter in vitro and as evidenced by increased plasma rosuvastatin levels when eltrombopag and rosuvastatin were co-administered in a clinical drug interaction study. When co-administered with eltrombopag, a reduced dose of rosuvastatin should be considered and careful monitoring should be undertaken. In clinical trials with eltrombopag, a dose reduction of rosuvastatin by 50% was recommended for co-administration of rosuvastatin and eltrombopag. Concomitant administration of eltrombopag and other OATP1B1 substrates should be undertaken with caution.

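### Section 5.5.2's flat 25 mg/day liver step leaves no usable first reduced dose for East and South East Asian children aged 2 to 5 weighing up to 20 kg

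*Combined protocol and SAP*

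**What the plan says.** Section 5.5.2 has two paragraphs, one for Cohorts 1 and 2 and one for Cohort 3, the Extension Cohort and the Laboratory Exploratory Cohort.

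- **Cohorts 1 and 2.** If ALT exceeds 6 times the upper limit of normal and a second test confirms it, the drug is stopped until ALT is below 5 times the limit. Then: "Eltrombopag will be restarted at a dose level 25 mg/day lower than the prior dose".
- **Later cohorts.** A rise in Days 1 to 14 leads to a hold and a restart at the same dose. A reduction follows only if ALT rises again, the rise "is not attributable to other inciting factors such as serum sickness, sepsis, or azole antifungal agents", and repeat tests confirm it. Then: "Then eltrombopag will be restarted at a dose level that is 25 mg/day lower than the prior dose".

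Both paragraphs repeat the 25 mg/day step if ALT rises again. Neither has an age qualifier or a lowest dose. Section 5.10 sends liver abnormalities from a cyclosporine interaction to the same rule: "eltrombopag will be dose-reduced according to Section 5.5.2".

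The platelet rule in Section 5.4 does distinguish by age: "In children under 12, the dose will be decreased by 12.5 mg". For East and South East Asian subjects, Section 5.3 says that "for children between 2 and 5, the starting dose will be 1.25 mg/kg". Section 4.1.3 requires a weight above 12 kg.

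**The concern.** The step is fixed in milligrams, while the starting dose for the youngest children is set by weight and is halved for East and South East Asian ancestry. For the smallest of these children the step is larger than the dose, so the instruction to restart has no dose attached to it. An investigator would have to leave the drug off or borrow the 12.5 mg step from the platelet rule, and two investigators could reasonably choose differently.

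The same step also makes very unequal proportional cuts across age groups, and the protocol gives no reason for that. Because Section 5.4 already has a smaller step for children under 12, this looks like an oversight.

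**Working it through.** The plan states no figure to reproduce; the check is direct arithmetic.

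**Inputs.** Starting doses are from Section 5.3 and Table 3, the weight limit from Section 4.1.3, the 25 mg step from Section 5.5.2 and the 12.5 mg step from Section 5.4.

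**Formula.** First reduced dose = starting dose - step. For children aged 2 to 5, starting dose = mg/kg × weight. Weights shown as 12 kg are the limit; eligible children lie just above it.

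| Group | Start (mg) | After one 25 mg step | Cut | After one 12.5 mg step |
|---|---|---|---|---|
| East/South East Asian 2-5, 12 kg | 1.25 × 12 = 15 | -10 | over 100% | 2.5 |
| East/South East Asian 2-5, 16 kg | 1.25 × 16 = 20 | -5 | over 100% | 7.5 |
| East/South East Asian 2-5, 20 kg | 1.25 × 20 = 25 | 0 | 100% | 12.5 |
| East/South East Asian 6-11 | 37.5 | 12.5 | 67% | 25 |
| Non-Asian 2-5, 12 kg | 2.5 × 12 = 30 | 5 | 83% | 17.5 |
| Non-Asian 2-5, 20 kg | 2.5 × 20 = 50 | 25 | 50% | 37.5 |
| Non-Asian adult | 150 | 125 | 17% | not applicable |

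The weight at which the first step gives exactly zero is 25 / 1.25 = 20 kg. A second 25 mg step takes the East and South East Asian 6-11 group to 12.5 - 25 = -12.5 mg.

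**Sachet rounding.** Section 5.3 says that a child who "needs a dose of 28 mg, then dose only single sachet that provides 25 mg dose". If the prior dose means the dose actually given, the result stays at 25 - 25 = 0 mg up to 28 / 1.25 = 22.4 kg. If it means the calculated dose, a 22.4 kg child would go from 28 to 3 mg. The text does not settle this, so 20 kg is the firm limit.

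**How many children.** Section 11.1 expects 6% Asian and roughly 20% under 18. Assume that age and ancestry are independent, that everyone recorded as Asian takes the lower dose, and that no weight limit applies. If ages 2 to 17 are evenly spread, 4/16 of minors are aged 2 to 5; as an upper case take one half.

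- Whole trial: 207 × 0.06 × 0.20 × 4/16 = 0.62; with one half, 1.24.
- One primary cohort of 31: 31 × 0.06 × 0.20 × 4/16 = 0.09; with one half, 0.19.
- Places left at the last extension: Section 2.9.4 says "We currently have accrued 178/182 patients to our protocol", which suggests 4 open places. Two of the 182 were Cohort 2 places never used (Section 2.9.1), and 86 of the 87 Extension places were filled. That leaves 1 + 25 = 26, roughly. Expected: 26 × 0.06 × 0.20 × 4/16 = 0.08; with one half, 0.16.

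All these counts are before any ALT trigger.

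**The case against.** **Other sections already stop the drug.** Section 9.6 discontinues it for intolerance that dose reduction has not settled. The label text in Section 11.4.3 calls for permanent discontinuation if liver abnormalities persist, worsen or recur. Section 5.3 allows interruption at the investigator's discretion. This largely stands: a reader might infer that the protocol leaves such a child without a safe course, and the documents do not support that. But none of these places gives a paediatric liver step or a lowest dose, and the Section 9.6 item presupposes a reduction that can be made.

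**The two rules address different hazards.** High platelets and liver injury need not share a step, and a larger cut for liver injury is defensible given the boxed warning in Section 11.4.3. A difference in step size alone would therefore not be an error. A step larger than the dose is not explained this way.

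**The first restart is not always affected.** A reader might infer that any first restart in these children would be at zero. In Cohort 3, the Extension and the Laboratory cohorts, a Day 1 to 14 hold is followed by a restart at the same dose. The problem there arises at the first reduced restart.

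**The Cohort 1 and 2 paragraph is mostly spent.** By 15 September 2014, 57 of the eventual 62 subjects were enrolled (Section 2.9.2). Drug under this protocol ends with five-year follow-up, and this version is dated March 2020. That stands and sets the priority for the fix.

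**The 12.5 mg step is only a partial cure.** Just above 12 kg on 1.25 mg/kg it still cuts 12.5 / 15 = 83%, and a second step gives 2.5 - 12.5 = -10 mg. At 20 kg the second step gives 12.5 - 12.5 = 0 mg. That stands too, so the stop-at-zero sentence is the essential part.

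**Conclusion.** Wrong as written, and minor. For East and South East Asian children aged 2 to 5 weighing up to 20 kg, the first liver dose reduction gives zero or less, and Section 5.5.2 still directs a restart. Other children under 12 take proportionally much larger cuts than an adult on 150 mg. The dose arithmetic needs no assumptions beyond the protocol's own figures.

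The size is small: about 0.6 to 1.2 children of 207 in the zero-dose row, and about 0.08 to 0.16 among the roughly 26 places left. These rest on the assumptions stated with the calculation and come before a confirmed ALT rise. Children still in their 6-month course, or restarted after relapse under Section 5.7, could also meet the rule.

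Two stronger readings are tempting and not supported. One is that children could be overdosed: the literal rule errs toward less drug, and leaving it off is a safe default. The other is that the 6-month complete response analysis is affected: with about 0.09 to 0.19 such children expected per cohort of 31, before any trigger, the effect is negligible.

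**What to change.** In Section 5.5.2, at least in the paragraph for Cohort 3, the Extension and the Laboratory cohorts:

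- use a 12.5 mg step for children under 12, as in Section 5.4; and
- state that eltrombopag stays permanently discontinued if a reduction would bring the dose to zero or below.

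Amending the Cohort 1 and 2 paragraph in the same way is reasonable for consistency but matters less.

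Reaching zero should not become the definition of persistent hepatotoxicity in Section 9.6: an adult on 150 mg would need 150 / 25 = 6 reductions to get there, which could delay a stop. At most, correct that item's cross-reference from Section 5.3, which contains no such definition, to Section 5.5.2.

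The cost is one clause and one sentence per paragraph, plus one section number, in the next amendment. No new procedure or supply is needed: Section 12.1 already lists 12.5 mg tablets and a 2 mg/mL suspension measured by syringe.

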5.6 Dose Delays, Modifications or Discontinuation of Eltrombopag for Hematologic Side Effects

5.6.1 Thrombosis/Embolism: Subjects who experience a deep venous thrombosis (other than a line-related upper extremity thrombosis) or a pulmonary embolus, a TIA or stroke, or a myocardial infarction at any time while on eltrombopag will discontinue eltrombopag but remain on CsA and hATG. Subjects with platelet counts of $> 50,000/\mu\text{L}$ at the time of thrombosis will be treated with enoxaparin or another appropriate anticoagulant as clinically indicated until the platelet count drops below $20,000/\mu\text{L}$ or they complete a standard 3-6 month course of anticoagulation.

5.7 Extended Access to Study Drug

Responders:

Cohorts 1 and 2: Study drug (eltrombopag) administration will be discontinued at 6 months for subjects in cohort 1 and at 3 months* for subjects in cohort 2; cyclosporine will be discontinued at 6 months for both cohorts.

Cohorts 1 and 2 Subjects that Relapse:

In cohort 2, if a subject who received eltrombopag for 3 months* has evidence of relapse as defined in Section 7, eltrombopag and/or cyclosporine can be restarted at the clinical investigator's discretion. Such cohort 2 subjects, who require treatment prior to month 6, will be denoted as non-responders at 6 months

for statistical purposes.

Subjects in cohort 1 or 2 that relapse (defined in section 7) after the end of 6-month treatment period while in follow-up may have eltrombopag and/or cyclosporine restarted at the clinical investigator's discretion. Subjects in cohort 2 that received the reduced CsA dose (2mg/kg/day) starting after the 6-month landmark visit who relapse despite the prolonged reduced dose of CsA may have the CsA dose increased to achieve therapeutic levels (trough levels 200-400) at the clinical investigator's discretion. Subjects can remain on the drugs under this protocol until the end of the 5 year follow-up period.

*Study drug (eltrombopag) administration will be discontinued at 3 months for subjects in cohort 2, except for subjects experiencing dose delays/interruptions as outlined in Section 5.3.

Cohort 3 and Extension Cohort:

Subjects that relapse (defined in section 7) after the end of 6-month treatment period while in follow-up may have eltrombopag restarted at the clinical investigator's discretion. In addition, the cyclosporine dose may be increased to achieve a therapeutic level. Subjects can remain on the drugs under this protocol until the end of the 5-year follow-up period.

Laboratory Exploratory Cohort:

Follow up for subjects in this cohort will be the same as Cohort 3 and Extension Cohort (above).

5.8 Pre-medications and Management of Infusion Reactions

Subjects will receive pre-medication approximately 30 minutes prior to infusion of ATG as follows:

- oral diphenhydramine 1 - 1.5 mg/kg/dose (NTE 50 mg) administered orally or intravenously, and;
- oral acetaminophen 10-15 mg/kg/dose (NTE 650 mg)

Oral prednisone at 1 mg/kg/d will begin prior to the first dose of h-ATG for serum sickness prophylaxis, and will be continued for 10 days total and then tapered over the subsequent 7-14 days. Infusion reactions will be treated symptomatically (e.g., antiemetics, IV fluid hydration, acetaminophen, antihistamines, inhaled bronchodilators, meperidine). Prednisone dose will be calculated based on actual body weight.

In case of moderate or severe reactions hydrocortisone will be given and the infusion will be discontinued and restarted at a slower rate once the symptoms have subsided. If a subject has a persistent severe infusion reaction that does not respond to measures to ameliorate the signs/symptoms associated with the infusion, the h-ATG infusion will be discontinued (see section off study criteria) and subjects will go off study.

5.9 Permitted Supportive Care

- Transfusion support (blood and platelets) as clinically indicated.
- Hematopoietic growth factors (e.g., G-CSF, GM-CSF, or erythropoietin) if deemed necessary by the investigator or treating physician. Romiplostim (N-Plate) or IL-11 (Neumega) should not be administered.
- Estrogens or combination OCP's as indicated for uterine bleeding

5.10 Concurrent Medications:

Cyclosporine/magnesium: Subjects will be on chronic CsA therapy targeting a stable drug level as long

as eltrombopag is administered 4 hours after oral magnesium given to counteract magnesium-wasting on CsA. Magnesium supplementation will not be given concurrently with eltrombopag as it may interfere with eltrombopag's absorption. The drug-drug interaction potential between eltrombopag and CsA is unknown. Both CsA and eltrombopag are inhibitors of OATP and BCRP drug transporters, and eltrombopag is a substrate of BCRP in vitro. It is not known if the combination will result in any PK changes to either drug. Subjects will be monitored for signs of CsA toxicity during the study, and therapeutic drug monitoring can be instituted as required. In the event of liver function abnormalities as a consequence of a drug-drug interaction between eltrombopag and CsA, eltrombopag will be dose-reduced according to Section 5.5.2.

Rosuvastatin: In vitro studies demonstrated that eltrombopag is not a substrate for the organic anion transporter polypeptide, OATP1B1, but is an inhibitor of this transporter in vitro and as evidenced by increased plasma rosuvastatin levels when eltrombopag and rosuvastatin were co-administered in a clinical drug interaction study. When co-administered with eltrombopag, a reduced dose of rosuvastatin should be considered and careful monitoring should be undertaken. In clinical trials with eltrombopag, a dose reduction of rosuvastatin by 50% was recommended for co-administration of rosuvastatin and eltrombopag. Concomitant administration of eltrombopag and other OATP1B1 substrates should be undertaken with caution.

Inhibitors of cytochrome p450: In vitro studies demonstrate that CYP1A2 and CYP2C8 are involved in the oxidative metabolism of eltrombopag. Trimethoprim, gemfibrozil, ciprofloxacin, fluvoxamine and other moderate or strong inhibitors of CYPs may therefore theoretically result enhanced activity of eltrombopag, however these interactions have not yet been established in clinical studies. All subjects on cyclosporine require prophylaxis against PCP and will be given inhaled pentamidine instead of TMP/SULF. NIH SAA patients are routinely placed on pentamidine instead of TMP/SULF for PCP prophylaxis to avoid potential marrow-suppressive effects of TMP/SULF anyway. Subjects aged 5 years and over will receive pentamidine for PCP prophylaxis but children under 5 years of age (approximate) are often not able to complete the inhalation treatment with pentamidine and will receive dapsone or another prophylactic regimen. Other CYP inhibitors can be used concomitantly but with careful attention to possible increased eltrombopag activity and toxicity.

Other medications: Subjects may continue on any of the medications that they were prescribed prior to study enrollment for co-morbid conditions, with the exception of N-Plate and Neumega (see 5.9).

